**Multicenter double-blind placebo-controlled parallel-group randomized
clinical trial of efficacy and safety of Subetta in the treatment of
impaired glucose tolerance**

Phase III

Sponsor	ООО «NPF «MATERIA MEDICA HOLDING»
Protocol number	MMH-SU-006
Version date:	May 30, 2019
ClinicalTrials.gov Id:	NCT03725033

Protocol Summary

This document represents the protocol summary for the study on human subjects. The study will be carried out in accordance with ICH GCP, National Standard of the Russian Federation GOST 52379-2005 "Good Clinical Practice", Helsinki Declaration of World Medical Association, relevant requirements of the regulatory authorities as well as the study procedures.

Title of Study

Multicenter double-blind placebo-controlled parallel-group randomized clinical trial of efficacy and safety of Subetta in the treatment of impaired glucose tolerance.

Phase: III

Sponsor: OOO "NPF "MATERIA MEDICA HOLDING", Moscow, Russia

Protocol No. MMH-SU-006

Objective of the study

- To assess efficiency and safety of Subetta in the treatment of impaired glucose tolerance¹ (IGT).

Endpoints

Primary endpoint

1. Changes in 2-hour fasting plasma glucose (OGTT²) at 12 weeks versus baseline.

Secondary endpoints

1. Percentage of subjects with 2-hour plasma glucose <7.8 mmol/L after 12-week therapy.
2. Changes in fasting plasma glucose at 12 weeks versus baseline.
3. Changes in HbA1c at 12 weeks versus baseline.

Safety assessment

- Presence and nature of adverse events during the therapy, their intensity (severity), relation to the product, outcome
- Percentage of patients with clinically relevant laboratory abnormalities after 12-week therapy
- Changes in vital signs.

¹ **Impaired glucose tolerance (IGT)** is a condition characterized by plasma glucose concentration of 7.8 to 11.0 mmol/L 120 min after oral glucose tolerance test (OGTT), with fasting plasma glucose <7.0 mmol/L.

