² **Oral glucose tolerance test (OGTT)** should be carried out in the morning against regular diet and regular physical activity. The test should be preceded by an overnight fast (8-14 hours, water allowed). A carbohydrate-containing meal (30-50g) should be consumed on the evening before the test. Once fasting blood has been drawn, the patient should consume 75g anhydrous glucose (or 82.5g glucose monohydrate) in 250-300 ml water for 5 minutes. Smoking is prohibited during the test. Repeat blood samples are taken after 2 hours. Plasma glucose test will be made in central laboratory, therefore to avoid glycolysis and wrong results the blood should be collected into a tube containing preservative (sodium fluoride) provided by the sponsor.

Study design

Design: a multicenter, double-blind, placebo-controlled, parallel-group randomized trial.

The study will enroll outpatients adults aged 18-70 years with impaired glucose tolerance (IGT) who did not receive glucose-lowering agents previously. Persons with pre-diabetes³, obesity (especially with visceral or abdominal obesity), dyslipidemia (with high triglycerides and/or low-density lipoproteins), hypertension, diabetes in first-degree relatives will be considered as potential candidates to participate in the study.

After the patient's information sheet and the form of informed consent for participation in the study are signed on the screening (visit 0; day from -7 to 0), complaints and history are collected, registration of concomitant conditions and diseases, objective examination, calculation of body mass index (BMI), oral glucose tolerance test (OGTT), fasting blood glucose. Furthermore, blood samples⁴ (for testing HbA1c, chemistry and hematology, HLA genotyping) and urine sample will be collected; concomitant therapy will be recorded, diet and physical activity recommendations will be given. All women of childbearing potential will be administered pregnancy tests.

If eligibility criteria are met and there are no non-inclusion criteria on Visit 1 (Day 1), the patient is randomized to one of two groups: the Subetta group (patients will take 2 tablets twice a day for 12 weeks) or placebo group (patients will take a placebo according to the scheme of Subetta for 12 weeks).

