In the course of the study, two more visits in 4 (Visit 2) and 12 (Visit 3) weeks are planned, during these weeks complaints are recorded, a patient's examination is recorded, therapy compliance and safety are assessed. On Visit 3 OGTT, fasting blood glucose, blood samples (for HbA1c, chemistry and hematology) and urinalysis will be performed.

The duration of observation period shall be up to 13 weeks.

During the study the treatment for underlying conditions will be allowed with the exception of the drugs indicated in the section "Prohibited concomitant therapy".

Inclusion and exclusion criteria

Inclusion criteria

1. Outpatients aged 18 to 70 years.
2. Impaired glucose tolerance (plasma glucose from 7.8 to 11.0 mmol / L 2 hours after a 75 g oral glucose consumption during an oral glucose tolerance test, while fasting plasma glucose <7.0 mmol / L).

³ **Prediabetes:** Fasting plasma glucose = 6.1–6.9 mmol/L or and 2) 2-hour plasma glucose post-OGTT = 7.8–11.0 mmol/L or/and 3) HbA1c 5.7–6.4%.

⁴ All investigations are carried out in a central laboratory.

3. HbA1c is 5.7–6.4%.
4. The body mass index is 25.0-39.9 kg / m².
5. Consent to use reliable contraceptive methods during the study (for men and women with reproductive potential).
6. The presence of the signed informed consent form to participate in the clinical trial.

Exclusion criteria

1. Type I or II diabetes mellitus.
2. Use of any medications indicated in the section “Prohibited concomitant medications”.
3. Acute or exacerbation/decompensation of chronic disease of any etiology at the time of examination or during the previous week.
4. Uncontrolled arterial hypertension with blood pressure: systolic blood pressure > 160 mm Hg and/or diastolic blood pressure > 100 mm Hg.
5. Acute coronary syndrome, myocardial infarction, acute impairment of cerebral circulation during the previous 6 months prior to enrollment.
6. Unstable or life-threatening arrhythmia during the previous 3 months prior to enrollment.
7. Acute and chronic heart failure with functional class III or IV (according to the classification of the New York Heart Association, 1964).
8. Respiratory failure.
9. Chronic kidney disease (classes C3-5 A3).
10. Hepatic insufficiency (class C according to Child-Pugh).
11. Presence or suspicion of oncology disease.
12. The presence of an allergy / hypersensitivity to any component of the medication administered during the treatment.

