 - glucagon-like peptide receptor analogues (GLP-1): exenatide, liraglutide, lixisenatide, dulaglutide, etc.
 - sodium-dependent glucose cotransporter type 2 inhibitors (SGLT2): dapagliflozin, empagliflozin, canagliflozin
2. Insulins and their analogs
3. Glucocorticosteroids for systemic use and topical glucocorticosteroids
4. Thyroid hormones
5. Oral contraceptives
6. Danazol
7. Chlorpromazine
8. Beta-2-sympathomimetics for injections
9. Appetite-stimulating drugs
10. Drugs for treatment of obesity
11. Nitric oxide release modulators, including nebivolol
12. Nitric oxide donators (long-acting nitrates and nitrate-like agents, except for on-demand nitrates used in angina episodes)
13. Diuretics
14. Biologically active food supplements
15. Phytochemicals
16. Products manufactured by Materia Medica Holding (Divaza, Impaza, Afalaza)
17. Drugs known to have caused allergic reactions

Study design scheme

Schedule of study procedures

Procedure	Visit	Visit 0 (Day -7 to 0) Screening	Visit 1 (Day 1) Screening, randomization	Visit 2 (Week 4±3 days)	Visit 3 (Week 12±3 days)
Informed consent		+			
Study subject registration in IVRS and assignment of a personal code		+			
Collection of complaints		+	+	+	+
Medical history		+			
Registration of co-morbid conditions and diseases		+	+		
Physical examination		+	+	+	+
Registration of vital signs (heart rate, respiratory rate, blood pressure)		+	+	+	+
BMI calculation		+			
Concomitant therapy		+	+	+	+
Eligibility assessment		+	+		
Randomization of the study subject			+		
Study drug supply			+	+	
Study drug accountability and return, compliance assessment				+	+
Recommendations (good nutrition and regular physical activity)		+	+	+	+
Evaluation of treatment safety			+	+	+
End of visit		+	+	+	+

Completion of the patient's participation in the study				+
Investigations:				
OGTT*	+			+
Blood sampling for HbA1c	+			+
Blood sampling for HLA genotyping	+			
Blood and urine samples for safety analysis	+			+
Pregnancy test**	+			
* Fasting blood glucose will be determined at OGTT (prior to glucose loading)				
** If applicable				

Statistical Analyses.

SAS 9.4 will be used for data processing and statistical calculations⁶.

Samples

Total set: all patients included in the study who have signed Informed Consent Form for participation in the study. All AEs including those occurred prior to the study therapy will be considered throughout the study for this sample.

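### The laboratory safety endpoint is a Week 12 prevalence with no within-patient comparison to Visit 0, so persisting abnormalities can dilute a difference between arms

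*Combined protocol and SAP*

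**What the plan says.** The Safety assessment list in the protocol summary gives the laboratory endpoint as "Percentage of patients with clinically relevant laboratory abnormalities after 12-week therapy". The neighbouring items are framed differently. The vital-sign item is "Changes in vital signs", and a secondary efficacy endpoint that is also a laboratory value is "Changes in HbA1c at 12 weeks versus baseline".

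Baseline laboratory data exist. At screening, under Study design, blood is drawn "for testing HbA1c, chemistry and hematology, HLA genotyping) and urine sample will be collected". At the end of treatment, "On Visit 3 OGTT, fasting blood glucose, blood samples (for HbA1c, chemistry and hematology) and urinalysis will be performed". The Schedule of study procedures has a row for "Blood and urine samples for safety analysis", marked at Visit 0 and Visit 3 only.

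On who may enter, Study design says that people with pre-diabetes, obesity, "dyslipidemia (with high triglycerides and/or low-density lipoproteins), hypertension, diabetes in first-degree relatives will be considered as potential candidates". Exclusion criterion 9 is "Chronic kidney disease (classes C3-5 A3", and criterion 10 covers hepatic insufficiency only at Child-Pugh class C.

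On analysis, the Safety parameters section deals with adverse events only. Data presentation promises that categorical variables will be tabulated as frequencies by visit. Neither section defines a clinically relevant abnormality, sets a treatment-emergent rule for laboratory data, or plans a shift table.

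**The concern.** Read as written, the endpoint is a point prevalence at Week 12. A patient with a clinically relevant abnormal result at Visit 0 and the same result at Week 12 can be counted exactly like a patient who became abnormal on treatment. A patient who was abnormal at entry and clearly worsened cannot be told from one who stayed the same.

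The entry criteria leave room for this. Patients with dyslipidemia, obesity or hypertension may enrol, and the kidney and liver exclusions name only the classes given above.

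Safety is one of the two parts of the stated objective. If both arms carry a common block of persisting abnormalities, two similar Week 12 percentages could be reported as reassurance although new abnormalities differ several-fold.

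**Working it through.** **Plan's own figures.** No sample size or rate is given for the laboratory endpoint. The only usable size is the primary-endpoint calculation in Evaluation of sample size, which reproduces:

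- 2 × (1.960 + 0.842)² × 3.11² / 1.1² = 125.48; × R of 1.1334 = 142.2, rounded up to 143 per arm.
- 286 / (1 − 0.66) = 841.2, rounded up to 842.

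The number of safety-population patients with a Week 12 sample is not stated. 143 per arm is the planned number of per-protocol completers. 421 per arm (842 / 2) is an upper bound, because 842 is the number signing consent and includes screening failures.

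**Assumptions (none is in the documents).** Let b be the share abnormal at Visit 0, s the share of those still abnormal at Week 12, and q the new-onset rate among patients normal at Visit 0. Take q = 10% on drug and 2% on placebo (true ratio 5), with b and s equal in both arms.

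**Formulas.** Week 12 prevalence = b·s + (1 − b)·q. Power is the two-sided 0.05 normal approximation for two proportions: Φ{[d − 1.96·√(2p̄(1 − p̄)/n)] / √([p₁(1 − p₁) + p₂(1 − p₂)]/n)}, where d is the absolute difference between p₁ and p₂, and p̄ is their mean. New abnormalities use n(1 − b) per arm.

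**Worked case, b = 20%, s = 1, n = 143.**

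- Drug: 0.20 + 0.80 × 0.10 = 28.0%. Placebo: 0.20 + 0.80 × 0.02 = 21.6%. Ratio 1.30.
- Power, Week 12 prevalence: (0.064 − 0.1001) / 0.0509 = −0.71, so 0.24.
- Power, new abnormalities, n = 114.4: (0.080 − 0.0615) / 0.0310 = 0.60, so 0.72.

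**All three cases, s = 1, 143 per arm.**

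| Abnormal at Visit 0 | Week 12 prevalence, drug v placebo | Observed ratio | Power, Week 12 prevalence | Power, new abnormalities |
|---|---|---|---|---|
| 10% | 19.0% v 11.8% | 1.6 | 0.39 | 0.77 |
| 20% | 28.0% v 21.6% | 1.3 | 0.24 | 0.72 |
| 40% | 46.0% v 41.2% | 1.1 | 0.13 | 0.60 |

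**Sensitivity.**

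- Fisher's exact test. With about 2 expected new abnormalities on placebo (0.02 × 114.4 = 2.3 at b = 20%), the plan's own rule under Non-parametric criteria points to Fisher. Power for prevalence against new abnormalities is then 0.33 / 0.72, 0.20 / 0.67 and 0.10 / 0.49.
- Denominator. Counting new abnormalities over all 143 per arm gives 0.77, 0.72 and 0.59.
- Partial persistence, s = 0.8. At b = 20%: 0.16 + 0.08 = 24.0% v 0.16 + 0.016 = 17.6%, ratio 1.36. At b = 40%: 0.32 + 0.06 = 38.0% v 0.32 + 0.012 = 33.2%, ratio 1.14.
- Larger sample. With 421 per arm and b = 20%, power is 0.58 against 0.99.
- Smaller signal, 6% v 2% (true ratio 3). The observed ratio is 1.31, 1.15 and 1.06 at b = 10%, 20% and 40%. Fisher power for new abnormalities at 143 per arm is only 0.25, 0.21 and 0.13.

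The dilution appears in every case with b above zero. The gain in power depends heavily on the size of the signal assumed.

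**The case against.** A reader might infer that the plan ignores Visit 0 altogether. It does not: tabulating categories by visit would put the Visit 0 rate beside the Week 12 rate, so someone seeing 28.0% v 21.6% would also see about 20% in each arm at entry. This stands, and it narrows the point to the missing within-patient comparison. It does not remove it, because new abnormalities offset by resolved ones leave the totals unchanged.

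A reader might also infer that every pre-existing abnormality will be scored as an on-treatment finding. The documents do not settle this. *Clinically relevant* is undefined, and an investigator could judge a stable, known abnormality not relevant. No rule requires or forbids that. Nor are the chemistry analytes listed, so it is an assumption that lipid results feed this endpoint. Dyslipidemia, obesity and hypertension describe potential candidates, not required features, and no Visit 0 abnormality rate is given.

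A third tempting reading is that the endpoint favours the drug. Randomization should balance pre-existing abnormalities, so the effect is dilution in both arms and not bias toward one.

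Finally, no hypothesis test is specified for this endpoint, so the power figures measure discriminating ability and not a planned decision. They evaluate new abnormalities only, not new or worsened ones. Adverse event reporting is a second route by which a signal could surface, although the documents do not say that laboratory changes are recorded as adverse events. These limits all stand.

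**Conclusion.** The point holds in limited form. The endpoint is a Week 12 prevalence, and no within-patient comparison with Visit 0 is specified anywhere, although the data for one are collected. Persisting abnormalities can therefore raise both absolute rates and shrink the contrast between arms, and worsening from an abnormal baseline is invisible.

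The size cannot be fixed from the documents. The illustrated fall from a ratio of 5 to between 1.6 and 1.1 rests on assumed new-onset rates, an assumed 10% to 40% abnormal at entry, full persistence, and investigators counting stable abnormalities as clinically relevant. It would be too strong to say that a signal will be hidden, or that the fix would reliably detect one: at 6% v 2%, Fisher power stays between 0.13 and 0.25 with 143 per arm. The gain is mainly in what the percentage means. This is a worthwhile, low-cost improvement to the safety analysis that does not touch the primary efficacy conclusion.

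**What to change.** - Redefine the endpoint as the percentage of patients in the safety population with a new or worsened clinically relevant laboratory abnormality versus Visit 0. *New* means not clinically relevant at Visit 0 and clinically relevant at Week 12. *Worsened* means clinically relevant at both visits with deterioration.
- State how *clinically relevant* and *worsened* are determined, and by whom, before unblinding. Without this the new wording inherits the present ambiguity.
- State the denominator, and show by arm how many patients lack a Visit 0 or Week 12 result.
- Add a Visit 0 by Week 12 shift table by arm.
- Keep the Week 12 prevalence as a descriptive line.

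The cost is endpoint and analysis wording plus one table. No samples, visits or patients are added.

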Safety population: all patients who received at least one dose of the study drug. This sample will be used for the study treatment **safety and tolerability analyze**, since all the AEs identified after the study drug administration will be recorded.

Full Analysis Set. This sample includes all enrolled and randomized patients, except for those who met at least one of the following criteria:

- 1) non-compliance with inclusion / exclusion criteria;
- 2) the patient has not taken as minimum a single dose of the study drug;
- 3) lack of any data of the patient after prescription of the study drug.

This sample is the most consistent with the “Intention-to-treat” principle, will be used for the **Intention-to-treat analysis (ITT analysis) of the the study therapy efficacy**.

Per protocol set. This sample includes all patients who completed the therapy as per the study protocol without any missing scheduled visits. This sample will be used for the **Per Protocol analysis (PP- analysis) of the the study therapy efficacy**.

Per Protocol set will not include the patients whose data are completely or partially invalid for analysis due to a protocol deviation.

Protocol deviations that lead to complete or partial data invalidity:

1. Violation of visit schedule.
2. Inappropriate distribution/supply of the study drug.

⁶ Licensee: OOO "NPF "Materia Medica Holding", No. 70100045

3. Administration of prohibited therapy.
4. Increase or decrease $\geq 25\%$ in the amount of the study therapy administered.
5. Inability to assess the patient's compliance using the formula (e.g. loss of pack with the product).
6. Major discrepancies between source documents and CRF detected during monitoring or another authorized check.
7. Violation of the procedure for obtaining Informed consent.
8. Non-compliance with the clinical study protocol procedures.
9. Inability to collect all patient's data used for evaluation of the study endpoints (e.g. lack of entries in source documents required for verification of inclusion/exclusion criteria, safety and efficacy criteria).
10. Other protocol deviations resulting in full or partial data invalidity.

Evaluation of sample size

The sample size has been assessed on the basis of the following rules and assumptions:

1. Statistical provisions.
 - 1.1 the power of the statistical tests " $P = (1 - \beta)$ " is assumed to be 80% (the probability of correct rejection of the null hypothesis is 0.8);

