 - 1.2 the probability of a type I error " α " is allowed to be less than 5% (the probability of the erroneous acceptance of an alternative hypothesis is less than 0.05);
 - 1.3 the statistical tests are 2-sided unless otherwise specified;
 - 1.4 the calculation of the sample size is based on the assumptions about the expected effects, declared in the primary efficacy endpoint of the Protocol;
 - 1.5 the ratio between the sample sizes of Subetta and Placebo groups is 1:1 (1 Subetta patient - 1 Placebo patient);
 - 1.6 statistical hypotheses - null and alternative hypotheses on superiority of the study product over placebo under the dosing regimen used
 - 1.7 one unblinded interim analysis on 50% sample was expected allowing to terminate the study both due to the effect confirmation (according to O'Brien-Fleming) and due to acceptance of null hypothesis (Pocock).

a) primary endpoint:

$$H_0: \Delta\mu_1 - \Delta\mu_2 = 0$$

$$H_a: \Delta\mu_1 - \Delta\mu_2 \neq 0$$

where $\Delta\mu_1$ - mean reduction (initial – final score) in Subetta group,

$\Delta\mu_2$ – mean reduction (initial – final score) in Placebo group;

1.8 calculation of sample size for statistical criteria will be made using the following formula:

$$n_1 = kn_2$$
$$n_2 = R \frac{(z_{\alpha/2} + z_{\beta})^2 * (1 + 1/k) * \sigma^2}{\epsilon^2}$$

where n_1, n_2 is sample size in IP and placebo groups, respectively

$\epsilon = \Delta\mu_1 - \Delta\mu_2$ is expected difference between mean reductions of value between Subetta and Placebo groups

k – coefficient of Subetta/Placebo sample ratio (1 : 1)

σ – standard deviation of reduction

$z_{\alpha/2}$ – tabular value of two-sided z-test for α

z_{β} – tabular value of one-sided z-test for β , R-coefficient taking into account interim analysis depending on the accepted functions of error and analysis position (in this design equal to 1.1334).

1.9 terminal sample size was determined using the formula:

$$N_T = N_{PP} / (1 - R_w)$$

where N_T – terminal sample size

N_{PP} – result of calculation in cl. 1.8, i.e. scheduled number of subjects completing the study per protocol

R_w – withdrawal rate.

2. Assumptions on expected clinical study effects: difference in reduction of 2-hour plasma glucose (at OGTT) between Product and Placebo groups will be no less than $\epsilon = 1.1$ at standard deviation of $\sigma = 3.11$.

A priori estimates for tested parameter variables in the groups:

Primary endpoint:

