Changes in 2-hour fasting plasma glucose (OGTT) at 12 weeks vs. baseline.

Placebo group:

characteristics of 2-hour plasma glucose level (at OGTT) at the start of the study.

SD=0.94 [39]

After 3 months

SD=2.3 [1.87; 2.987] [40]

Change (3 m) -0.2 [-1; 0,6] [40]

Standard deviation of change in 3 months (in assumption of independence of scoring for DM)

SD_Δ~311.

Study drug group:

Based on interim study, change in glucose level in experimental group in 3 months was:

Change (3 m) = 1.96 [1,7; 2,22]

Let us take standard deviation of change in experimental group similar to control group.

Software code for evaluation of sample size:

Proc seqdesign errspend;

Design nstages=2

Info=cum(0.5,1)

Method(alpha)=UNI(rho=0.5 tau=0)

Method(beta)=UNI(rho=0 tau=0)

Stop=both

Alpha=0.05

Beta=0.2;

Samplesize model=twosamplemeans(meandiff=1.1 stddev=3.11);

Run;

Therefore, the value of expected effect is rated as $\epsilon_{\Delta}=1.1$ mmol/L (the most conservative scoring) – the worst case for Subetta and the best for Placebo) at standard deviation $\sigma_{\Delta}=3.11$ mmol/L. Thus, sample size will be 143 subjects per study group. Taking into account the claimed withdrawal coefficient, this will require enrollment of 842 subjects.

Therefore, overall size of the required sample will be 842 subjects ensuring the study completion per protocol by at least 286 subjects.

Therefore, the sample size has been found to be (143) patients in each of the groups (Product and Placebo) to estimate superiority of the study drug over placebo.

Taking into account potential withdrawal of at least 66% subjects⁷ (Cw=0.66) during the study for various reasons, at least 842 patients should sign PIS and ICF.

Statistical criteria

All statistical calculations will be performed using two groups of statistical criteria:

- parametric – to obtain effective estimates for random parameters in case the relevant conditions of method/model applicability are not violated (e.g. sphericity, normality, risk proportionality, etc.);

⁷ Based on blinded interim analysis.

- non-parametric – in all other cases.

Parametric criteria

The application of parametric criteria will be accompanied by a check of models for applicability (e.g. Kolmogorov-Smirnov test, Shapiro-Wilk test).

The following parametric methods and approaches are to be used:

1. To assess the differences of continuous variables obtained in one group at two different visits – Student t-test for paired samples.

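### As implied by the design code, the interim futility region is symmetric, so a trial with Subetta about 0.52 to 1.38 mmol/L worse than placebo meets no stated stopping rule although superiority is very unlikely

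*Combined protocol and SAP*

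**What the plan says.** All references are to the combined protocol and SAP, section on evaluation of sample size.

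- Item 1.6 frames the question as "null and alternative hypotheses on superiority of the study product over placebo".
- Item 1.3 states that "the statistical tests are 2-sided unless otherwise specified", and the alternative for the primary endpoint is "H_a: \Delta\mu_1 - \Delta\mu_2 \neq 0". The first term is the "mean reduction (initial – final score) in Subetta group", so a positive difference favours Subetta.
- Item 1.7 reads "one unblinded interim analysis on 50% sample was expected allowing to terminate the study both due to the effect confirmation" (O'Brien-Fleming), "and due to acceptance of null hypothesis (Pocock").
- The printed SAS code sets two stages at information 0.5 and 1, alpha 0.05, beta 0.2 and stopping for either reason. The efficacy shape is "Method(alpha)=UNI(rho=0.5 tau=0"); the acceptance shape is the same family with rho 0. No one-sided alternative is requested.

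Neither item 1.7 nor the interim analysis section prints a boundary value, says in which direction acceptance of the null operates, or adds a rule for an unfavourable trend.

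**The concern.** In a two-sided design that can stop to accept the null, the acceptance region is a band around zero, and continuation zones lie on both sides of it. The upper zone is where a superiority trial should carry on. The lower zone holds results in which Subetta is clearly behind placebo, but not far enough behind to reject the null against it. Continuing there can hardly lead to a superiority finding. It can mainly establish that Subetta is worse, which is not an objective of the trial.

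The ordering is also odd: an interim result 0.3 mmol/L worse than placebo stops the trial, whereas one 0.8 mmol/L worse does not. At stake is the enrolment and treatment of up to the whole second half of the sample under an unfavourable trend.

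**Working it through.** **Inputs.** Difference 1.1 mmol/L, SD 3.11 mmol/L, alpha 0.05, 1:1 allocation, look at 50% information, O'Brien-Fleming efficacy shape, Pocock acceptance shape, R = 1.1334, 143 completers per arm and 66% withdrawal, all from the sample-size section. Power is 80% (item 1.1: "the probability of correct rejection of the null hypothesis is 0.8").

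**1. Reproduce the plan's figures.** Fixed design: n = 2 × [3.11 × (1.960 + 0.842)/1.1]² = 125.48 per arm.

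Two-stage design with information fraction t: efficacy bound |Z| = Ca/√t; acceptance bound |Z| = D√t − Cb; the two meet at the final analysis, so D = Ca + Cb. Solving for two-sided 5% and 80% power with a binding acceptance region gives Ca = 1.8826 and Cb = 1.1000, hence D = 2.9826.

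- R = 2.9826²/(1.960 + 0.842)² = 1.1334, as printed.
- n = 125.48 × 1.1334 = 142.2, so 143 per arm, as printed.
- 286/0.34 = 841.2, so 842, as printed.

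Other readings of the code:

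| Reading | R | Per arm |
|---|---|---|
| Two-sided 5%, binding | 1.1334 | 143 |
| One-sided 5%, binding | 1.157 | 115 |
| Two-sided 5%, non-binding | 1.208 | 152 |
| One-sided 2.5%, binding | 1.1334 | 143 |

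The last row shows that R alone does not settle sidedness. The printed alpha of 0.05 does: it yields 143 only if it is two-sided.

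**2. Interim regions.** Efficacy: 1.8826/√0.5 = 2.662. Acceptance: 2.9826 × √0.5 − 1.1000 = 1.009. With 71.5 per arm, SE = 3.11 × √(2/71.5) = 0.520 mmol/L, so the bounds are 0.52 and 1.38 mmol/L.

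| Interim difference (positive favours Subetta) | Rule |
|---|---|
| above +1.38 | stop, reject |
| +0.52 to +1.38 | continue |
| −0.52 to +0.52 | stop, accept null |
| −1.38 to −0.52 | continue |
| below −1.38 | stop, reject (favours placebo) |

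**3. Chance of final superiority given Z1.** The final Z is √0.5 × (Z1 + Z of the second half), and it must exceed 1.8826. For a true difference δ, conditional power = 1 − Φ(2.662 − Z1 − δ/0.520).

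| Z1 | Difference (mmol/L) | δ = 1.1 | δ = 0 |
|---|---|---|---|
| −1.009 | −0.52 | 6.0% | 0.012% |
| −1.5 | −0.78 | 2.0% | 0.002% |
| −2.0 | −1.04 | 0.5% | <0.001% |

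Under the observed trend the chance is effectively zero throughout this zone.

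**4. Chance of entering the lower zone.** Φ(−1.009 − δ/0.520) − Φ(−2.662 − δ/0.520):

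| True difference (mmol/L) | Probability |
|---|---|
| +1.1 | 0.09% |
| +0.55 | 1.9% |
| 0 | 15.3% |
| −0.55 | 46.5% |
| −1.1 | 57.4% |

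With no true effect, the upper zone also has probability 15.3%, so half of all continuations are on the unfavourable side.

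**5. Cost of closing the zone.** Under the planned effect, 3.74% of trials that continue in the lower zone end in superiority: 0.0892% × 3.74% ≈ 0.003 percentage points of power.

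**The case against.** **The rule is inferred.** Item 1.7 gives no direction and is permissive (it allows termination), the code is presented as sample-size code, and the document is a protocol summary. That stands as a limit on certainty. Still, only a binding acceptance region reproduces the printed R, and the alternative hypothesis, item 1.3 and the code all point to two sides.

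**Two-sided testing is a stated and conventional choice.** Correct. A reader might infer that item 1.6 contradicts item 1.3, but superiority is routinely tested two-sided at 5%. The point concerns the direction of the futility region, not the final test.

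**Continuation in the lower zone is informative.** If Subetta is truly 0.55 mmol/L worse, a trial that continues there has about a 52% chance of a significant result against Subetta (about 89% at 1.1 mmol/L worse). This is the real price of the change. It is acceptable only because showing inferiority to placebo is not an objective.

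**The harm scenarios have no basis in the documents.** Also fair: a true deficit of 0.55 mmol/L is illustrative. The no-effect figure of 15.3% does not depend on it.

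**The saving may be smaller.** No recruitment pause is stated, so fewer than 143 completers may be spared. At 66% loss, 143 completers correspond to 143/0.34 ≈ 421 consents, but screening failure is among the listed withdrawal reasons, so many of those people would never be treated.

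**A tempting stronger reading** is that two-sidedness also makes the trial stop at a mildly favourable trend. At Z1 = +1.009 conditional power under the planned effect is 68%, and results just below that do stop. But this follows from the Pocock shape of the acceptance boundary. A one-sided 2.5% design with the same shapes has the same bound of 1.009, so this is a separate issue that the present fix leaves unchanged.

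**Conclusion.** The point holds for the lower continuation zone. As implied by the hypotheses and code, an interim result with Subetta about 0.52 to 1.38 mmol/L worse meets no stated stopping rule, while the chance of final superiority is at most 6.0% under the planned effect and about 0.01% or less under no effect.

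Two stronger inferences are not supported. Superiority is not impossible in the zone, only very unlikely. Nor does the trial continue at every unfavourable result: deficits up to 0.52 mmol/L stop for acceptance of the null, and those beyond 1.38 mmol/L stop as a rejection.

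The figures assume SD 3.11, 143 completers per arm, a look at exactly 50% and a binding acceptance region. The weight is moderate: the zone is almost never entered if the planned effect is real, but it matters when there is no effect or a harmful one, and closing it costs almost nothing.

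**What to change.** In item 1.7, state that the futility bound applies in one direction: the trial may stop for futility at any interim Z in favour of Subetta below the bound, including all negative values. Print the bounds (1.009 and 2.662 under the present design) and say whether the futility bound is binding. Keep the two-sided 5% final test, so that the alternative hypothesis and items 1.2 and 1.3 need no rewriting. If the futility bound is later re-set for other reasons, the same one-directional reading should apply to it.

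**Cost.** The change needs a short addition to item 1.7. The sample size stays at 143 per arm, and superiority power falls by about 0.003 percentage points. The trial mostly gives up a formal final finding that Subetta is worse than placebo. If the true difference were −0.55 mmol/L and the interim efficacy bound were kept on both sides, the chance of such a finding would fall from about 29.8% (5.4% at the interim plus 46.5% × 52.45% = 24.4% at the end) to about 5.4%. Up to about 143 further completers are saved per avoided continuation, and fewer if recruitment runs on during the interim look.
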